4.1. Primary and secondary endpoint

Cure rate (CR) (primary endpoint, i.e. conversion from being egg positive pre-treatment to egg negative post-treatment) and egg reduction rate (ERR) (secondary endpoint). In addition, key pharmacokinetic parameters will be determined and safety of treatment evaluated (secondary endpoints).

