4.3. Trial design

4.3.1. Baseline survey

Stool samples collection

Two stool samples will be collected from each participant until a total of 560 hookworm-infected participants (160 preschool-aged children, 200 school-aged children and 200 adults) and 480 *T. trichiura* infected participants (160 preschool-aged children, 160 school-aged children and 160 adults) are identified.

[figure not shown]
The Kato-Katz technique will be used for the quantitative assessment of STH infections. Two stool samples will be collected from each participant before treatment and from each sample duplicate Kato-Katz thick smears (41.7 mg each) will be prepared [8]. The slides will be analyzed under a microscope by experienced technicians and a subsequent independent quality control of sample results (approximately 10%) will be conducted. Results are considered correct if the following tolerance margin is not exceeded: (i) No difference in presence/absence of hookworm, A. lumbricoides and T. trichiura, (ii) egg counts are +/-10 eggs for counts ≤100 eggs or +/-20% for counts >100 eggs (for each species separately) [9]. In case discrepancies above the tolerance margin are noted in one or more slides, all slides are re-read by the local technicians. The new results are discussed, so that in case of discordant results, slides can be re-evaluated to reach consensus. Infection intensity expressed as the arithmetic and geometric mean egg counts per gram of stool (EPG) will be calculated for each treatment arm. All microscopically analyzed quadruplicate Kato-Katz thick smears will be destroyed within one day (after passing the quality control). Since drug efficacy could be influenced by genetic aspects, ~2 g of stool sample from each participant will be preserved in ethanol for further genetic analyses of hookworm and T. trichiura in Côte d'Ivoire and Switzerland.

[figure not shown]
Clinical examination and biological exams

At baseline, the medical history of *T. trichiura* and hookworm-infected participants in the study will be assessed with a clinical and physical examination carried out by the study clinician, who will assess weight, height, body temperature, pulse rate and blood pressure. Rapid diagnostic tests for malaria will be done to assess the presence of a *Plasmodium* spp. co-infection. Hemoglobin (Hb) levels will be detected using HemoCue to exclude severely anemic participants (below 80 g/l and 70 g/l Hb in school-aged and preschool-aged children,

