4.4. Measure to minimize bias

Study participants eligible for treatment will be randomly assigned to one of the treatment arms using a computer-generated, stratified block randomization code. The random allocation sequence with varying random blocks of 4 and 8 (or 5 and 10, respectively) stratified by 2 levels of baseline infection intensity (light and moderate *T. trichiura* and hookworm infections) will be provided by a statistician. Study-site investigators will be aware

of the study group assignment, whereas participants and laboratory technicians will be blinded.

Placebo controlled trials reduce the risk of potential bias that can also interfere with the observed outcomes. In previous studies (e.g. Coulibaly et al. 2017 Lancet Global Health), we have observed moderate cure and egg reduction rates in placebo treated children likely due to the low sensitivity of anthelminthic diagnostics. Children treated with placebo will be treated at follow up (3-weeks post treatment) with 400 mg albendazole. This treatment delay does not cause any harm.

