5.2. Inclusion criteria

- 1. Male and female preschool-aged children (2-5 years), school-aged children (6-12 years) and adults (≥21 years) infected with *T. trichiura*/hookworm.
- 2. Written informed consent signed by study participant/parent/guardian and written assent in the case of school-aged children.
- Positive for *T. trichiura*/hookworm by at least two slides of the quadruple Kato-Katz thick smears and infection intensities of at least 100 eggs per gram of stool (EPG).
- 4. Agree to comply with study procedures, including provision of two stool samples at the beginning (baseline) and approximately three weeks after treatment (follow-up).

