7.3. Description of statistical methods

The primary analysis will use the full analysis set (available case population) according to the intention to treat principle defined as all randomized subjects which provide any follow-up data. Only subjects which were negative at baseline and erroneously randomized will be excluded from the analysis. In addition, a per-protocol analysis will be conducted. CRs will be calculated as the percentage of egg-positive participants at baseline who become egg-negative after treatment. EPG will be assessed by adding up the egg counts from the quadruplicate Kato-Katz thick smears and multiplying this number by a factor of six. The ERR will be calculated (ERR = (1-(mean at follow-up/mean at baseline))*100).

Geometric mean egg counts will be calculated for the different treatment arms before and after treatment to assess the corresponding ERRs. Bootstrap resampling method with 5,000 replicates will be used to calculate 95% confidence intervals (CIs) for ERRs point estimates. E_{max} models using the DoseFinding package of the statistical software environment R will be implemented to predict the dose-response curves in terms of CRs and ERRs.

On the basis of the LC-MS/MS measurements, the following PK parameters for plasma will be calculated:

C_{max} maximal plasma concentration

t_{max} time to reach C_{max}

AUC area under the curve, from 0 to 24h and 0 to inf

T_{1/2} elimination half-life

 C_{max} and T_{max} will be observed values derived from the plasma concentration time profile. AUC and $T_{1/2}$ will calculated with the software WinNonlin (Version 5.2, Pharsight Corporation, USA) using noncompartmental analysis. The elimination half-life will be estimated by the equation: $T_{1/2} = ln2/\lambda$, where λ will be determined by performing a regression of the natural logarithm of the concentration values during the elimination period.

Further PK analysis will be undertaken fitting a structural compartmental PK model with the software NONMEM 7 via nonlinear mixed effects modeling (allowing for both between patient variation and random effects). This model will describe the blood drug levels in time, allowing one to investigate variation between patients in drug levels. In addition, pharmacometric-pharmacodynamic (PKPD) analysis will be undertaken via NONMEM to investigate the drivers of cure and/or burden reduction and potentially any covariates with drug levels.

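### The smears that qualify a participant at 100 EPG or more also form the ERR baseline, so each arm's stand-alone ERR includes regression to the mean; report a placebo-referenced ERR beside it

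*Combined protocol and SAP*

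**What the plan says.** - **Entry.** Section 5.2 requires positivity on "at least two slides of the quadruple Kato-Katz thick smears and infection intensities of at least 100 eggs per gram of stool (EPG").
- **Baseline measurement.** Section 4.3.1 describes one pre-treatment set: "Two stool samples will be collected from each participant before treatment and from each sample duplicate Kato-Katz thick smears". Neither it nor the visit schedule in section 4.6 describes a second count after eligibility is settled. The qualifying count is therefore also the baseline count.
- **ERR.** Section 7.3 gives a within-arm before/after ratio, "The ERR will be calculated (ERR = (1-(mean at follow-up/mean at baseline))*100"), and says which mean feeds it: "Geometric mean egg counts will be calculated for the different treatment arms before and after treatment to assess the corresponding ERRs". Section 4.3.2 names arithmetic means as well. Bootstrap intervals (5,000 replicates) and an Emax curve are planned on these ERRs.
- **Placebo.** Every cohort has a randomized placebo arm (sections 3 and 10.6). Section 4.4 reports from previous studies that "we have observed moderate cure and egg reduction rates in placebo treated children likely due to the low sensitivity of anthelminthic diagnostics". Section 7.3 does not say how the placebo ERR enters the estimate of a dose's effect.
- **Status.** Section 4.1 lists "egg reduction rate (ERR) (secondary endpoint"); cure rate is primary.

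**The concern.** Selecting on a noisy count and then using it as the denominator builds in a fall. Among people admitted because four smears reached a threshold, some were having a high day. The follow-up smears carry no such selection, so the mean drops even if nothing was given.

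The stated ERR credits that drop to the dose. At stake is the level of egg reduction reported for each dose under the first secondary objective. Any descriptive comparison of age cohorts is also exposed, because the drop is larger where intensities lie nearer the threshold.

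**Working it through.** **Inputs from the documents.** Two stools with two 41.7 mg smears each; EPG is the egg sum times six; entry at 100 EPG or more with at least two positive slides; ERR as in section 7.3.

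**The plan's own conversion.** 1000 / (4 × 41.7) = 5.995, so the factor of six is right. The threshold then means at least 17 eggs over four slides (17 × 6 = 102; 16 × 6 = 96). The plan states no ERR figure to reproduce.

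**Assumptions (not in the documents).** Person-mean EPG lognormal with geometric mean 100–400 and log-SD 1.0–1.5; day-to-day gamma variation with shape 0.5–2; geometric mean taken as log(x+1). This gives 18 scenarios of 300,000 people. The entry rule is applied, then follow-up counts are drawn afresh.

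**Algebra.** Let r be the fall without drug and e the drug's proportional reduction.
- Raw ERR = 1 − (1 − r)(1 − e)
- Difference from placebo = (1 − r)e
- Placebo-referenced ERR = 1 − (1 − ERR_dose)/(1 − ERR_placebo) = e

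With r = 0.30 and e = 0.60, these are 1 − 0.70 × 0.40 = 0.72, 0.70 × 0.60 = 0.42, and 1 − 0.28/0.70 = 0.60.

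**Placebo arm, no drug.** ERR is 8–61% by geometric mean and 1–27% by arithmetic mean.

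**Drug cutting output by 60% and curing nobody (geometric mean).** Raw ERR is 64–85%, the difference from placebo is 24–56 points, and the placebo-referenced ERR is 61–62%.

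**Adding true cures, with a 60% cut in the rest.** Excess of the raw over the placebo-referenced geometric-mean ERR:

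| Cured | Excess (points) |
|---|---|
| 0% | 3–23 |
| 10% | 2–16 |
| 30% | 1–7 |
| 50% | 0–3 |

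At 30% cure, for example, the raw value is 92–95% against 88–92%. For active doses, section 7.2 assumes cure of 10–40% for *T. trichiura* and 30–80% for hookworm.

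**A second set of assumptions.** Median EPG 60–250, log-SD 1.0–1.5, lognormal day-to-day variation with log-SD 0.4–1.0, and slide dispersion k of 1–3 give a no-drug ERR of 7–60% (geometric) and 0.3–33% (arithmetic). A true 50% reduction without cures reads as 54–81% raw and 50.7–52.2% placebo-referenced (geometric).

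**How much is due to the threshold.** In that second model (log-SD 1.5, day-to-day log-SD 0.7, k = 1.5), admitting anyone with any egg gives a no-drug geometric-mean ERR of 16%, 9% and 4% at median 60, 120 and 250. With the plan's entry rule it is 30%, 24% and 17%.

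**Across cohorts.** Take the same 60% no-cure drug in cohorts with geometric mean 100 and 400 EPG (log-SD 1, gamma shape 1). Raw ERR is 77% against 68%. The difference from placebo is 38 against about 50 points. The placebo-referenced ERR is 62% against 61%. The first two scales rank the cohorts in opposite orders although the drug acts equally.

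**Dose-response.** ERR(d) = r + (1 − r)e(d) is linear in e(d). If e(d) is an Emax curve, so is ERR(d), with E0 = r and the same ED50. Fitting a true curve with maximum 0.95 and ED50 250 at r = 0, 0.1, 0.3 and 0.6 returned an ED50 of 250 each time, and a maximum divided by (1 − E0) of 0.95 each time.

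**The case against.** The strongest reply is that the trial already has the right control. Each cohort's placebo arm passes the same entry rule, allocation is stratified by baseline intensity, 0 mg is a design dose in section 7.2, and section 4.4 gives bias as a reason for using placebo. An ERR-scale Emax curve fitted with dose 0 takes the artefact into its intercept. That stands. A reader might infer that the artefact creates a false dose-response, reorders the doses or invalidates the Emax analysis. The documents do not support that, because the fall is common to all arms of a cohort.

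Four further limits also stand:
- The large excesses belong to a drug that cures few people, and they shrink quickly at the cure rates the plan assumes for hookworm.
- The arithmetic-mean artefact is much smaller, and section 4.3.2 plans that mean too.
- Section 7.3 plans no formal comparison of ERR between age groups, and which cohort is lighter is unknown. The cross-cohort distortion is therefore descriptive and of unknown direction.
- The placebo-referenced geometric-mean ERR is not the reduction in mean egg output once some people are cured. With 30% cured and 60% reduction in the rest, mean output falls by 1 − 0.7 × 0.4 = 72%, while the geometric-mean ratio gives 88–92% and varies with intensity.

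What the reply leaves open is the reported level. Section 7.3 reports each arm's raw ERR, does not refer it to placebo, and does not say on which scale such a reference would be made. Section 4.4 attributes the placebo fall to diagnostic sensitivity. Whatever its source, a fall shared with placebo is not drug effect.

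**Conclusion.** The point holds for the level of the secondary ERR endpoint. Each arm's stand-alone ERR overstates the drug-attributable reduction, and a simple difference from placebo understates it. By geometric mean, the overstatement is roughly 2–16 points at 10% cure and no more than about 3 points at 50%, so it matters mainly in low-cure arms such as those assumed for *T. trichiura*. These sizes rest wholly on assumed egg-count variability and on a 60% reduction in those not cured; the structural argument does not.

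A reader might go further and conclude that the trial's efficacy findings are compromised. They are not: the cure-rate formula does not divide by the baseline count, and the dose ranking and the ERR-scale ED50 are preserved. This is a cheap improvement to reporting, not a design fault.

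**What to change.** In section 7.3:

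1. Keep the within-arm ERR as a descriptive figure and show the cohort's placebo ERR beside it.
2. For each dose, add a placebo-referenced ERR: 1 − [(follow-up mean / baseline mean) in the active arm ÷ (follow-up mean / baseline mean) in the concurrent placebo arm of the same cohort]. Give it for both geometric and arithmetic means, with the planned 5,000-replicate bootstrap resampling both arms.
3. Keep the planned ERR-scale Emax model with placebo as dose 0, and report the dose effect as (ERR(d) − E0)/(1 − E0). A refit on the log ratio is not needed and would change the meaning of the ED50: the check curve with ED50 250 fits there at about 667.
4. State that the geometric-mean version is not the reduction in mean egg output when some participants are cured.

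The cost is a few sentences and a few lines of code, with no new data. The placebo-referenced ERRs will look lower than raw ERRs, and their intervals will be somewhat wider because placebo variability enters.

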standardized questionnaire (for preschool-aged children this will be administered to the caregiver of the child). In addition a clinical examination will be performed by the study physician and venipuncture to examine biochemical parameters in the blood will be carried out by study nurses before treatment. Adults, children and caregivers of preschool-aged children will also be interviewed before treatment, 3 and 24 hours after treatment, and at follow-up (2-3 weeks after treatment) about the occurrence of adverse events. The efficacy of the treatment will be determined 14-21 days post-treatment by collecting another two stool samples. All stool samples will be examined with duplicate Kato-Katz thick smears. A subsample of children and adults will be sampled using finger pricking for micro-blood sampling at 0, 1, 2, 3, 4, 6, 8, 24 hours post-dosing to evaluate pharmacokinetic parameters. **Statistical Analyses** An available case analysis (full analysis set according to the intention to treat principle) will be performed, including all subjects with primary endpoint data. Supplementary, a per-protocol analysis will be conducted. CRs will be calculated as the percentage of egg-positive subjects at baseline who become eggnegative after treatment. Geometric mean egg counts will be calculated for the different treatment arms before and after treatment to assess the corresponding ERRs Bootstrap resampling method with 5,000 replicates will be used to calculate 95% confidence intervals (CIs) for ERRs. E_{max} models using the DoseFinding package of the statistical software environment R will be implemented to predict the dose-response curves in terms of CRs and ERRs. Noncompartmental and nonlinear mixed-effects (NLME) modeling will be used to determine PK parameters. **GCP** statement This study will be conducted in compliance with the protocol, the current version of the Declaration of Helsinki, ICH-GCP E6 (R2) guidelines as well as all national legal and regulatory requirements. **Key explanation for the** This study will be carried out in children, since an infection with T. inclusion of children trichiura and hookworm occurs most often in children and they are the main targets of preventive chemotherapy programs. Moreover, the exact dosage of albendazole in preschool and school-aged children has not yet been determined. Recruitment procedure Participants will be recruited from rural communities situated in Côte d'Ivoire and identified to have at least a moderate infection risk (prevalence: 10-49%) of *T. trichiura* or hookworm.

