4.3.2. Assessment of efficacy after treatment

The efficacy of the treatment will be determined 14-21 days post-treatment by collecting another two stool samples which will be microscopically examined for *T. trichiura* and hookworm and for co-infections (*A. lumbricoides*) using duplicate Kato-Katz thick smears.

Participants will be considered *T. trichiura* and hookworm cured if no eggs have been found in the stool. EPG will be assessed by adding up the egg counts from the quadruplicate Kato-Katz thick smears and multiplying this number by a factor of six. Geometric and arithmetic mean egg counts will be calculated for the different treatment arms before and after treatment to assess the corresponding ERRs.

At the end of the study, all participants remaining positive for *T. trichiura* or hookworm will be treated with 400 mg albendazole, the current standard treatment.

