7.2. Justification of number of trial subject

Since the existence of a drug effect is well known, the main aim of the study is the elucidation of the nature of the dose–response relationship. A series of simulations was carried out to determine the required sample size. We assumed a true cure rate against hookworm of 5%, 30%, 50%, 70% and 80% (for 0, 200, 400, 600 and 800 mg) and of 5%, 10%, 20%, 30% and 40% against *T. trichiura* and loss to follow up of 5%. We estimated that enrolling 40 participants per arm will be sufficient to predict the dose response curve with a precision (defined as median distance between prediction and confidence band) of about 10 percentage points. The suggested sample size is also in line with the recommendations from Klingenberg et al. 2009 [11]. This sample size is sufficiently high to determine the key PK parameters as well as PK/PD relationships.

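### Does the missing rule for zero egg counts in the geometric-mean egg reduction rate require a change to the plan?

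*Combined protocol and SAP*

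**What the plan says.** Section 7.3 defines the measure as "ERR = (1-(mean at follow-up/mean at baseline))*100" and states which mean is used: "Geometric mean egg counts will be calculated for the different treatment arms before and after treatment to assess the corresponding ERRs". The synopsis repeats the geometric mean. Section 7.3 then gives the ERR a bootstrap confidence interval with 5,000 replicates and adds Emax models, which "will be implemented to predict the dose-response curves in terms of CRs and ERRs".

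Section 4.3.2 is slightly wider: "Geometric and arithmetic mean egg counts will be calculated for the different treatment arms before and after treatment to assess the corresponding ERRs". It also defines a participant as "cured if no eggs have been found in the stool", so every cured participant has a follow-up count of 0 EPG. Counts are summed over four slides and multiplied by six, so the smallest non-zero value is 6 EPG. Section 5.2 requires at least 100 EPG at entry, so zeros arise only at follow-up.

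No section gives an additive constant or any other treatment of zeros.

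**The concern.** Read literally, the formula breaks down. One cured participant makes the arm's geometric mean 0 and its ERR 100%, even under placebo. Some convention must be supplied, and the ERR takes a different value under each.

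The placebo arm looks most exposed because it anchors the Emax curve. Section 4.4 says of earlier studies that "we have observed moderate cure and egg reduction rates in placebo treated children likely due to the low sensitivity of anthelminthic diagnostics". Each such zero raises the geometric placebo ERR by an amount that the constant sets. Section 7.2 names the shape of the dose-response as the main aim, so a constant chosen after the data are seen could alter the starting level and steepness of one of the two planned curves. The bootstrap interval would carry the chosen constant without reflecting the choice.

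**Working it through.** **Plan's own figures.** Arms of 40: hookworm 4 + 5 + 5 = 14, *T. trichiura* 4 + 4 + 4 = 12. That is 26 arms and 26 × 40 = 1040, as stated. Simulated Emax fits to the cure rates gave a median band half-width of 8.9 to 11.4 points across cohorts, which agrees with the stated precision of about 10. Neither figure involves the ERR.

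**How likely zeros are.** With 5% loss, 40 × 0.95 = 38 are evaluable per arm. P(at least one zero) = 1 − (1 − CR)^38, where CR is the cure rate assumed in section 7.2:
- CR 5%: 85.8% (six placebo arms, 38 × 0.05 = 1.9 zeros expected)
- CR 10%: 98.2%
- CR 20%: 99.98%

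All 20 active arms are therefore at 98% or above.

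**Effect of the constant.** For baseline m, reduction r in the uncured and constant c:

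ERR = 1 − [exp{(1 − CR) ln(m(1 − r) + c) + CR ln c} − c] / m

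The documents give neither m nor r. Assumed: m = 100, 400 or 800 EPG; r = 0 under placebo; in active arms r is 50% throughout, 80% throughout, or rising 20/40/60/80% over 200 to 800 mg. The constants compared are 1 and 6 (one egg on four slides).

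Placebo, CR 5%, m = 400:
- c = 1: exp(0.95 × ln 401) − 1 = 296.2; ERR = 1 − 296.2/400 = 26.0%
- c = 6: exp(0.95 × ln 406 + 0.05 × ln 6) − 6 = 322.9; ERR = 1 − 322.9/400 = 19.3%

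Hookworm 200 mg, CR 30%, r = 20%:
- m = 400: 86.0% (+1) against 76.9% (+6), a gap of 9.1 points, the largest at this baseline
- m = 100: 79.3% against 67.3%, a gap of 12.0 points, the largest anywhere at the planned cure rates

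For hookworm at 400 mg or more with m = 400, the gap is at most 4.5 points. The four distinct dose layouts (school-aged and adult cohorts share theirs), three patterns of r and three baselines make 36 combinations. The ERR rises with dose in all 36 under both constants.

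**Effect on the fitted curve.** Least-squares fit of E0 + Emax·d/(ED50 + d) to these expected ERRs, with ED50 bounded at 0.001 to 1.5 times the top dose:

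| Cohort | Pattern | ED50 at 400 EPG, +1 / +6 (mg) | Ratio +6 to +1, 100–800 EPG |
|---|---|---|---|
| Hookworm, school-aged/adult | 50% | 43 / 68 | 1.51–1.60 |
| | rising | 67 / 118 | 1.73–1.85 |
| | 80% | 19 / 27 | 1.25–1.45 |
| *T. trichiura*, school-aged/adult | 50% | 200 / 234 | 1.05–1.21 |
| | rising | 352 / 555 | 1.53–1.70 |
| | 80% | 64 / 64 | 0.88–1.05 |
| *T. trichiura*, preschool | 50% | 165 / 149 | 0.80–0.94 |
| | 80% | 39 / 31 | 0.73–0.85 |

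Preschool hookworm behaves like the first block (1.2 to 1.85). In preschool *T. trichiura* with rising reductions, the +6 fit sits at its upper bound, so its ratio is not informative. The shift in ED50 thus has no fixed direction. At 400 EPG every hookworm ED50 in the table lies below the lowest active dose of 200 mg, where the trial has no data.

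**The case for a change.** The strongest case for a change is that it costs a sentence and closes off a choice after the data are seen. It also holds that the effect can exceed what is shown above. Two parts of this stand.

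First, if placebo cure were 20% instead of the planned 5% (one assumed reading of moderate), the placebo ERR at 400 EPG would be 70% with +1 and 58% with +6. The gap of 12 points becomes about 15 at 100 EPG (60.9% against 46.3%).

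Second, more extreme constants widen the spread. With an assumed log-normal baseline cut off at 100 EPG and 5% cure, the placebo ERR is 33–36% at c = 0.1, 25–28% at 1, 18–21% at 6 and 12–15% at 25. Neither 0.1 nor 25 is a natural choice for counts in multiples of six; 1 and 6 are.

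The largest contrasts that can be drawn do not bear on the missing constant. For hookworm with rising reductions, the ED50 is 67 mg with +1 and 602 mg with the arithmetic ERR. That compares geometric with arithmetic means, and section 7.3 and the synopsis have already chosen the geometric. The same texts answer which ERR is the main one; section 4.3.2 only adds the arithmetic version beside it.

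It remains true that the constant is not fixed in writing. But nothing can be won by choosing it: the plan sets no test, threshold or dose-selection rule on the ERR, and the order of doses does not depend on it.

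**Conclusion.** The plan omits a convention; it does not contain an error. The literal formula fails so visibly, with a 100% ERR in any arm with one cure, that no analyst could apply it unnoticed. The remedy is routine: add a constant before taking logs and subtract it after back-transformation. Writing that down would confirm what would be done anyway, and any constant remains a convention. The arithmetic ERR of section 4.3.2 needs no constant and already gives a check on the geometric one.

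At the planned cure rates, +1 against +6 moves an arm's ERR by at most 12 points, and by about 7 under placebo. The ED50 of the secondary ERR curve moves up to 1.9-fold for hookworm and in either direction for *T. trichiura*. These sizes rest on assumed baselines of 100 to 800 EPG and assumed reductions in the uncured; a placebo cure rate well above 5% would enlarge the placebo shift. Under all of these assumptions the dose ordering, the primary cure-rate analysis and the sample size stay as they are. No change to the plan follows.

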4.3.3. Pharmacokinetic studies

Pharmacokinetic studies will be performed in a maximum of 20 participants per treatment arm (520 patients in total). Upon oral intake, albendazole gets metabolized first to sulfoxide and further to sulfone, whereas the sulfoxide is thought to be the most active compound to treat STH infection. In order to evaluate potential differences of PK parameters, including the metabolization rate in different populations, all three compounds, namely albendazole, albendazole sulfoxide and albendazole sulfone, will be quantified with time. Two blood microsampling techniques, namely dried blood spot (DBS) and Mitra® are currently under investigation to quantify albendazole and its metabolites in human blood samples. Consequently, whole blood, plasma, DBS and Mitra® blood samples were collected in a previous clinical trial in rural Côte d'Ivoire with 10 adult volunteers who received the standard dose of albendazole. Methods to extract and quantify albendazole and its metabolites in all four matrixes are currently validated in order to demonstrate that the capillary and venous blood results correlate satisfactoryly. Once validation of the analytical method has been completed, the best blood micro-sampling device, DBS or Mitra®, will be chosen as a tool for these albendazole population pharmacokinetic studies in preschool-aged children, schoolaged children and adults.

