7.1. Definition of primary endpoint

Cure rate is the primary outcome of our study. Since these might be influenced by infection intensity, treatment allocation will be stratified by baseline infection intensity.

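### Allocation is stratified by baseline infection intensity, but the planned Emax cure model names no stratum term; if intensity predicts cure, the reported band is slightly conservative with respect to the strata

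*Combined protocol and SAP*

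**What the plan says.** Section 7.1 gives the reason for stratifying, speaking of cure rates: "Since these might be influenced by infection intensity, treatment allocation will be stratified by baseline infection intensity". Section 4.4 gives the form: permuted blocks, "stratified by 2 levels of baseline infection intensity (light and moderate" for both species).

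For the analysis, the synopsis (Statistical Analyses) begins with crude rates: "CRs will be calculated as the percentage of egg-positive subjects at baseline" who are egg-negative after treatment. Section 7.3 repeats this and adds that Emax "models using the DoseFinding package of the statistical software environment R will be implemented to predict the dose-response curves in terms of CRs" and of ERRs. Neither place names a stratum or a baseline-intensity term, and neither rules one out.

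Baseline intensity appears in two other places. Section 4.3.1 uses it as a description of the arms: "Infection intensity expressed as the arithmetic and geometric mean egg counts per gram of stool (EPG) will be calculated for each treatment arm". Section 7.3 also plans a separate NONMEM analysis "to investigate the drivers of cure and/or burden reduction and potentially any covariates with drug levels".

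Section 7.2 justifies 40 participants per arm by the Emax band itself, with a "precision (defined as median distance between prediction and confidence band) of about 10 percentage points".

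**The concern.** The design treats intensity as possibly prognostic for cure, and the stated primary analysis does not. Stratified blocks balance intensity across the arms. A model without the stratum still counts cure differences between strata as unexplained variation between participants, so its band claims no credit for that balance.

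Band width is the quantity on which the trial bases its sample size, so the effect can be measured on the plan's own criterion. The stratum must be known before a participant can be randomised, so using it needs no new data. What is at stake is a small amount of reported precision and a modelling choice that is better settled before the data are seen.

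**Working it through.** **Inputs from the documents (section 7.2).** 40 per arm with 5% loss gives 40 × 0.95 = 38 evaluable. Assumed cure rates at 0/200/400/600/800 mg are 5/30/50/70/80% for hookworm and 5/10/20/30/40% for *T. trichiura*. Doses per cohort are as in section 3.

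**Assumptions not in the documents.** A 95% band; Emax on the logit scale; a light-versus-moderate odds ratio (OR) for cure of 1, 2, 3 or 5; 50% or 20% of participants in the moderate stratum. Overall cure rates are held at the section 7.2 values.

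**Models.**
- Without stratum: logit p(d) = e0 + emax·d/(ed50 + d).
- With stratum: the same plus b·s, where s = 1 for moderate. The curve is then standardised: p(d) = (1 − w)·p_L(d) + w·p_M(d), with w the pooled moderate share.
- Both are fitted by maximum likelihood with a delta-method band. Precision is the median half-width over the dose range, with 250 simulated trials per scenario.

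**Step 1: reproduce the plan's figure.** Without a stratum term and at OR 1, the half-width is 9.54 points (hookworm, five arms), 10.98 (hookworm, preschool), 10.19 (*T. trichiura*, school-aged and adults) and 9.18 (*T. trichiura*, preschool). The stated figure of about 10 is reproduced.

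**Step 2: add the stratum (50% moderate; half-widths in points).**

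| Cohort | OR | Without | With, mix sampled | Gain | With, mix fixed | Gain |
|---|---|---|---|---|---|---|
| Hookworm, five arms | 2 | 9.53 | 9.46 | 0.07 | 9.38 | 0.15 |
| Hookworm, five arms | 5 | 9.53 | 9.25 | 0.28 | 8.99 | 0.54 |
| Hookworm, preschool | 2 | 11.01 | 10.92 | 0.09 | 10.88 | 0.13 |
| Hookworm, preschool | 5 | 11.01 | 10.63 | 0.38 | 10.33 | 0.68 |
| *T. trichiura*, school-aged/adult | 2 | 10.18 | 10.10 | 0.08 | 10.04 | 0.14 |
| *T. trichiura*, school-aged/adult | 5 | 10.14 | 9.95 | 0.19 | 9.73 | 0.41 |
| *T. trichiura*, preschool | 2 | 9.10 | 9.06 | 0.04 | 9.01 | 0.09 |
| *T. trichiura*, preschool | 5 | 9.16 | 8.96 | 0.20 | 8.74 | 0.42 |

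At OR 1 the sampled-mix differences are 0.01 to 0.03 points, which is chance fit. With 20% moderate and OR 5 the sampled-mix gains are 0.22, 0.25, 0.11 and 0.08 points in cohort order. A separate run of 600 trials for preschool hookworm at OR 5 and 50% moderate gave 11.15 without the term, 10.73 with the mix sampled (gain 0.42) and 10.36 with it fixed (gain 0.79).

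**Step 3: analytic check, mix fixed.** The width factor is √(1 − R²), with R² = w(1 − w)(p_L − p_M)²/[p(1 − p)]. At p = 0.5 and w = 0.5:
- OR 2: p_L = 0.586, p_M = 0.414, R² = 0.029, factor 0.985.
- OR 5: p_L = 0.691, p_M = 0.309, R² = 0.146, factor 0.924.

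On an 11-point band this is about 0.2 and 0.8 points, the upper end of the fixed-mix gains.

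**Step 4: why the sampled-mix column is the fair comparison.** The band without the stratum refers to the population, including uncertainty about which mix was recruited. Treating the mix as known removes that part. Restoring it adds w(1 − w)(p_L − p_M)²/N to the variance. For preschool hookworm at OR 5, N = 4 × 38 = 152 and the fixed-mix variance is (0.1033/1.96)² = 0.002778.
- Stratum gap at a 30% cure rate (R² = 0.116): (p_L − p_M)² = 0.116 × 0.21/0.25 = 0.0974. The addition is 0.25 × 0.0974/152 = 0.000160, and the half-width is 1.96 × √0.002938 = 10.6 points.
- Stratum gap at 50% (squared gap 0.146): the addition is 0.000240, and the half-width is 1.96 × √0.003018 = 10.8 points.

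The simulated values, 10.63 and 10.73, lie in this range.

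**Step 5: does the curve itself improve?** Hardly. At OR 5 and 50% moderate, the trial-to-trial SD of the fitted curve goes from 4.70 to 4.66 points, 5.21 to 5.14, 4.71 to 4.75 and 3.55 to 3.56 in cohort order. In other runs the largest fall was about 0.2 points.

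**The case against.** The strongest reply is that nothing stated in the plan fails. The precision target is met without the term, stratified blocks already deliver the balance that section 7.1 sought, and an unadjusted population-average curve is a legitimate choice. The association with cure is only conjectured, and every visible gain depends on an assumed odds ratio near 5. All of this stands. It makes the point an improvement and not a correction.

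A second reply also stands in part: at one dose the band is not too wide to begin with. The assumed hookworm rates do not lie exactly on a logit-Emax curve. In simulations of 2,000 trials per scenario (moderate share 10 to 50%), the unadjusted band covered the true rate at 400 mg in 87.7 to 93.7% of trials. Coverage there was 88.4% in the five-arm cohort with no stratum effect at all. With the stratum and a fixed mix it was 86.9 to 92.4%, and the largest drop at any trial dose was from 91.9 to 89.6%. This shortfall comes from the curve shape and not from the strata, but a narrower band makes it slightly worse. A band that allows for sampling of the mix is wider than the fixed-mix band around the same curve, so it gives up less.

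It might also be said that the NONMEM analysis covers intensity. It does not fill the gap: "Pharmacokinetic studies will be performed in a maximum of 20 participants per treatment arm", against 40 randomised per arm, and it is a separate secondary analysis.

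A reader might infer that leaving out the stratum biases the dose-response curve or makes the sample size inadequate. The documents do not support either reading. Stratified allocation keeps intensity balanced across arms, and the stated precision is reproduced without the term. Nor do they support saying that the plan excludes adjustment; it is silent.

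**Conclusion.** The point holds as a cheap improvement of low priority. Allocation uses baseline intensity and the stated Emax cure model does not. If intensity predicts cure, the reported band is conservative with respect to the strata by about 0.04 to 0.1 percentage points at an odds ratio of 2 with half the cohort moderate (less with a smaller moderate share). At an odds ratio of 5 the excess is up to about 0.4 points. Both are set against a target of about 10.

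A figure near 0.8 points arises only if the cohort's stratum mix is treated as fixed, which is not a like-for-like comparison with the unadjusted band. At an odds ratio of 1 there is no gain. No bias is involved, and no conclusion about the shape of the curve would change.

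The sizes rest on an assumed odds ratio, moderate share, logit-scale Emax form and 95% band, none of which the documents give. The direction needs only that intensity predicts cure.

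**What to change.** In section 7.3 and the matching synopsis line:
- Include the randomisation stratum (light or moderate) as a term in the binomial, logit-scale Emax cure model for each cohort.
- Report the dose-response curve standardised to that cohort's pooled stratum mix, with a band that allows for sampling of the mix.
- Keep the crude cure rates by arm as reported tables.

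If the sponsor prefers the unadjusted curve, one sentence saying so before the data are seen would at least close the choice.

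The cost is two or three sentences and slightly more analysis work, with no new data and no change to sample size or procedures. The loss is negligible if intensity does not predict cure. The band also becomes slightly narrower at hookworm 400 mg, where the imperfect fit of the Emax shape to the assumed rates already holds coverage below 95%.
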